## **7.12. Analysis populations**

### **7.12.1. Screened population (SCR)**

The screened population consists of all subjects who signed informed consent.

### **7.12.2. Full analysis set (FAS)**

All subjects belonging to the screened population who received at least one dose of study drug. Efficacy and Safety analyses will be performed on FAS.

### **7.12.3. Per protocol set (PPS)**

All subjects included in FAS without any protocol deviation, which could impact the efficacy outcome. Those protocol deviations leading to exclusion from FAS and creating the PPS will be listed including the subject number and specified in the Protocol Deviation specification form.

### **7.12.4. PK analysis set (PKAS)**

All subjects included in FAS with at least one evaluable MOR202 serum concentration data.

### **7.12.5. Immunogenicity analysis set (IAS)**

All subjects included in SCR with at least one anti-drug antibody (ADA) result available.

### **7.12.6. Biomarker analysis set (BAS)**

All subjects included in FAS with at least one biomarker assessment available.

### **7.12.7. Planned analyses for the different populations**

The number of subjects in each analysis set will be summarized. A listing of all analysis sets for each subject will be prepared.

Table 7-1 gives an overview of the assessments performed on the different analysis sets.

**Table 7-1 Planned analyses for different populations**

Analysis	SCR	FAS	PPS	PKAS	IAS	BAS
Subject disposition	X	X				
Background and demographic characteristics		X				
Medical history and aMN-specific medical history		X				

**STATISTICAL ANALYSIS PLAN**

MorphoSys AG

MOR202C103

Analysis	SCR	FAS	PPS	PKAS	IAS	BAS
Study treatment		X				
Prior and concomitant medications and aMN-specific medical history		X				
Safety analysis during and after MOR202 treatment		X				
Best immunological response		X	X			
Immunogenicity of MOR202					X	
PK profile of MOR202				X		
Summary of 24 hour urine		X				
CCI		X	X			
		X	X			
		X				
		X				
		X				
		X				
		X				
Summary of vital signs, physical examination and ECG		X				
Summary of laboratory data		X				

**7.12.8. Withdrawal of informed consent**

The date on which a subject signs the main informed consent, additional informed consent for kidney biopsy at screening, additional informed consent for kidney biopsy at last study visit or additional informed consent for future research is recorded in the eCRF.

Any data collected in the clinical database after a subject withdraws the main informed consent from further participation in the trial, will not be included in the analysis data sets.

If a subject withdraws only any of the additional informed consents, the related data collected in the clinical database after the withdrawal, will not be included in the analysis data sets.

Exceptions are the information entered to close a page after the date of withdrawal of consent, e.g. End of Treatment or End of Study information.

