#### 8.4. Data included in the analysis and cut-off date

All the analyses will be performed using data collected in the database up to the data cut-off date. A cut-off date will be defined for each of these analyses and will be specified in the outputs.

Any data collected beyond the cut-off date will not be included in the analysis. Only data with an assessment date or event start date prior to or on the cut-off date will be included in the analysis.

All events with an event start date either before or on the cut-off date and an event end date after the cut-off date will be reported as “continuing at the cut-off date”. The same rule will be applied to events starting either before or on the cut-off date and not having a documented end date. This approach applies, in particular, to adverse event and concomitant medication reports. For these events, the end date will not be imputed and therefore will appear as missing in listings.

If it is required to impute an end date to be able to perform a specific analysis, the cut-off date needs to be imputed as an end date. The imputed date will be displayed and flagged in the listings.

Any data collected beyond a subject’s withdrawal of consent will not be included in the analysis; except for SAEs and the date of death provided by a confirmed public registry and subject status entered after the date of withdrawal of consent on e.g. early treatment discontinuation eCRF page.

The data before cut-off for the primary analysis includes all data until the last subject completes Cycle 6 of treatment, i.e. after the EOT visit, or 28 days after the last subject received the last dose of MOR202 for early terminated subjects.

Table 8-1 below indicates the analyses performed for the primary and final analyses.

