#### Treatment Emergent Adverse Event (TEAE)

TEAEs are defined as any adverse event reported within the following time interval (including the lower and upper limits), which is referred to as the treatment-emergent period:

[Start date of study drug, End date of study drug + 28 days].

The analysis of TEAEs will serve as primary endpoint of this trial.

If the start date and time of an AE are partially or completely missing, the AE will be assumed to be a TEAE if it cannot be definitely shown that the AE did not occur during the treatment emergent period

---

(worst case approach). Missing dates and times will not be replaced. The following approach will be followed:

- If the start time of an AE is missing but the start date is complete, an AE will only be excluded from TEAE if the start day is before the day of first study drug administration or the start date is after the end date of the treatment-emergent period
- If the start time and day are missing but the start month is complete, an AE will only be excluded from TEAE if the start month is before the month of first study drug administration or the start month is after the end month of the treatment-emergent period or if the stop date and time is before the start of first study drug administration
- If the start day and months are missing but the start year is complete, an AE will only be excluded from TEAE if the start year is before the year of first study drug administration or if the start year is after the end year of the treatment-emergent period or if the stop date and time is before the start of first study drug administration
- If the start date is completely missing, an AE will not be excluded from TEAE unless the stop date and time is before the start of first study drug administration

AEs starting during the study but before the first date of study drug administration will be classified as pre-treatment adverse events and will be presented in a separate adverse events listing.

An AE present prior to first study drug administration but increased in severity after treatment start, will also be included as TEAE.

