### **Post-Treatment Adverse Event**

Post-treatment AEs are defined as any adverse event reported within the following time interval (including the lower and upper limits), which is referred to as the post-treatment period:

[End date of study drug + 28 days + 1 day; Date of study discontinuation].

The analysis of post-treatment AEs will serve as one of the secondary endpoints.

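### SAP 7.12.8 and SAP 8.4 disagree on whether SAEs arising after withdrawal of consent are kept in the analysis; align and cross-refer them

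*SAP*

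**What the plan says.** Two sections of the current SAP text give a rule for data that arrive after consent is withdrawn.

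- **SAP 7.12.8** (Withdrawal of informed consent): whatever is recorded once a participant "withdraws the main informed consent from further participation in the trial, will not be included in the analysis data sets". It then lists what may stay: "Exceptions are the information entered to close a page after the date of withdrawal of consent, e.g. End of Treatment or End of Study information". SAEs and deaths are not on that list.
- **SAP 8.4** (Data included in the analysis and cut-off date): the same general exclusion, but "except for SAEs and the date of death provided by a confirmed public registry and subject status entered after the date of withdrawal of consent".

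Neither section cites the other or says which prevails.

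SAP 11.1 ties this to the main result: "The analysis of TEAEs will serve as primary endpoint of this trial". The treatment-emergent period is ["Start date of study drug, End date of study drug + 28 days"], both limits included, and it is not cut at withdrawal of consent. The post-treatment period, which serves a secondary endpoint, is ["End date of study drug + 28 days + 1 day; Date of study discontinuation"].

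**The concern.** The two rules give different answers for the same record. Suppose a subject withdraws main consent a week after an infusion and has a new SAE a week later. Under 8.4 the event is kept, and it falls in the treatment-emergent period. Under 7.12.8 it never reaches the analysis data sets, which SAP 8.5 says are the ADaM sets built before any output. Whether a serious event is tabulated would then depend on which section the programmer follows, and the choice could be made after the event is known. With about 20 and 10 subjects per cohort, one subject is visible in every safety percentage.

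**Working it through.** **1. The rules side by side**

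| Item recorded after withdrawal of main consent | SAP 7.12.8 | SAP 8.4 |
|---|---|---|
| Non-serious AEs, laboratory and efficacy data | excluded | excluded |
| Page-closing information / subject status | kept | kept |
| SAE | excluded (not among the exceptions) | kept |
| Date of death from a confirmed public registry | not named | kept |
| Death entered on the early study discontinuation page | arguably kept as page-closing information | arguably kept as subject status |

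The firm difference is the SAE row. The position on deaths is less sharp, because SAP 11.1.4 (Deaths) says death is also captured on the early study discontinuation page.

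**2. Can such an SAE fall in the primary window?** Yes.
- Planned doses are at most 28 days apart (SAP 7.1), so a subject on schedule who withdraws during treatment generally still has part of the last-dose-plus-28-days window left.
- Protocol 10.8.5 follows prematurely withdrawn subjects for AEs to at least 28 days after the last dose, so such events can be collected.
- Protocol 12.6 includes data from all dosed subjects when appropriate and has no separate rule on consent withdrawal, so it does not settle the matter.

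**3. The plan's own safety figures** (SAP 6.3, Protocol 12.5), reproduced first:
- Cohort 1: 1 − 0.90^20 = 0.878, stated as 88%.
- Cohort 2: 1 − 0.85^10 = 0.803, stated as 80%.

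Both reproduce, and the conflict does not alter them.

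**4. Size if one subject is affected.** Assume the subject has no earlier SAE and, for the intervals, that this is the only SAE in the group. Clopper-Pearson 95% limits: for 0/n the upper limit is 1 − 0.025^(1/n); for 1/n the limits are the 2.5% quantile of Beta(1, n) and the 97.5% quantile of Beta(2, n − 1).

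| Group | 7.12.8 followed | 8.4 followed | Change |
|---|---|---|---|
| Cohort 1 | 0/20, 0% (0 to 16.8) | 1/20, 5.0% (0.1 to 24.9) | 5 points |
| Cohort 2 | 0/10, 0% (0 to 30.8) | 1/10, 10.0% (0.3 to 44.5) | 10 points |
| Overall | 0/30, 0% (0 to 11.6) | 1/30, 3.3% (0.1 to 17.2) | 3.3 points |

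If the cohort already has SAEs in other subjects, the step is the same but the contrast is less stark: 2/20 against 3/20 in Cohort 1 is 10.0% (upper limit 31.7%) against 15.0% (37.9%).

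**5. Which rows move.** The SAE row moves if the subject had no earlier SAE. The maximum-grade row moves if the event is worse than anything that subject had before. The row for any TEAE moves only if the subject had no earlier TEAE.

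**6. How likely is it?** The documents give no rate of consent withdrawal. The Protocol synopsis expects about 10% to discontinue prematurely for all reasons, about 3 of 30, which serves here as an upper value. With k withdrawals and an assumed probability p of a new SAE in the rest of the window, the chance of at least one affected subject is 1 − (1 − p)^k:
- k = 1, p = 2%: 2%
- k = 3, p = 5%: 1 − 0.95^3 = 14%
- k = 3, p = 20%: 1 − 0.80^3 = 49%

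Both k and p are assumptions, so this is a range of scenarios and not an estimate.

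**The case against.** The best defence is that little turns on this. Several steps must line up: main consent is withdrawn, a new SAE then starts within 28 days of the last dose, and it is recorded in the clinical database. Safety oversight is not affected, since 7.12.8 governs analysis data sets only and Protocol 10.8.10 still requires prompt notification of related SAEs learned of after a subject has left. The AE tables in SAP 11.1.3 and 11.1.4 specify counts and percentages without intervals, although the Protocol synopsis promises 95% limits for trial endpoints generally. All of this stands, and it limits the size of the point. It does not remove the contradiction. Reading 8.4 as the governing section is possible, but 7.12.8 is the section devoted to consent withdrawal and has its own list of exceptions.

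Three stronger readings are tempting and not supported:

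- *All data after withdrawal are dropped under 7.12.8.* Page-closing information is excepted there.
- *Deaths are lost under one rule and kept under the other.* 8.4 keeps only a registry date of death, and a death recorded on the early discontinuation page may already be covered by the exception in 7.12.8.
- *The events dropped are the informative ones, because toxicity drives withdrawal.* Under Protocol 8.8.1 and 8.8.2, stopping for toxicity, or because the subject wishes to stop MOR202, is discontinuation of treatment, and the subject goes on to follow-up. Withdrawal from the trial is separate (Protocol 8.8.4) and calls for a complete final evaluation at that time. An event that prompted withdrawal starts before it; what is exposed is a new SAE afterwards.

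**Conclusion.** The inconsistency is real and lies in current SAP body text. It is clear for SAEs and weaker for deaths. For one affected subject with no earlier SAE, the SAE row differs by 5 points in Cohort 1, 10 points in Cohort 2 and 3.3 points overall, assuming the planned numbers of about 20, 10 and 30. A reader might infer that the primary safety results as a whole depend on which section is followed. That goes too far: non-serious AEs after withdrawal are excluded under both rules, and nothing changes unless such a subject occurs. The secondary endpoint on post-treatment AEs is less exposed, because its window closes at study discontinuation under either rule. This is an internal inconsistency with a conditional effect, worth correcting because it bears on how serious events are counted and costs almost nothing.

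**What to change.** Amend SAP 7.12.8 so that it carries exactly the exceptions in 8.4: SAEs, the date of death from a confirmed public registry, and subject status. State that retained SAEs and deaths enter the analysis data sets and are assigned to the AE and death outputs by the existing treatment-emergent and post-treatment windows, so an event outside both is not added to those tables. Cross-refer 7.12.8 and 8.4 so that one rule applies. If the sponsor wants to retain deaths from sources other than a registry, that would widen 8.4 and should be written as a deliberate change in both sections.

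The cost is a sentence or two in the SAP. No data collection, sample size or design figure changes. The amendment is best made before the final analysis data sets are built, so that the rule is not chosen with the events in view.

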## 7.13. Implementation of efficacy assessments

### 7.13.1. Renal function

Renal function will be assessed by the estimated glomerular filtration rate (eGFR). eGFR in ml/min/1.73m^2 will be calculated as per the Chronic Kidney Disease Epidemiology Collaboration (CKD-EPI) equation ((1), (2)):

$$eGFR = 141 \times \min\left(\frac{Scr}{\kappa}, 1\right)^\alpha \times \max\left(\frac{Scr}{\kappa}, 1\right)^{-1.209} \times 0.993^{Age} \times 1.018[\text{if female}] \\ \times 1.159[\text{if black}],$$

Where:

- Scr is serum creatinine in µmol/L,
- κ is 61.9 for females and 79.6 for males (if Scr is measured in µmol/L),
- (κ is 0.7 for females and 0.9 for males (if Scr is measured in mg/dL)),
- α is -0.329 for females and -0.411 for males,
- min indicates the minimum of  $\frac{Scr}{\kappa}$  or 1, and
- max indicates the maximum of  $\frac{Scr}{\kappa}$  or 1.

Stable renal function is defined in this trial by eGFR as an eGFR of at least 80% of baseline.

### 7.13.2. CCI

CCI

### 7.13.3. Overall response for subjects

#### Immunological Response

Immunological responses are reflected by the reduction of anti-PLA2R antibody titres as measured by ELISA (Euroimmun). Based on the immunological responses, the following response categories are defined for this clinical trial (the baseline value is the last measurement obtained prior to treatment start):

- Immunological Partial Response (IPR): Reduction of anti-PLA2R antibody titres by at least 50% compared to baseline
- Immunological Complete Response (ICR): Reduction of anti-PLA2R antibody titres to less than 14.0 RU/mL
- Stringent Immunological Complete Response (sICR): ICR and a negative result in anti-PLA2R immunofluorescence test

The following variables related to immunological responses are defined as follows.

## STATISTICAL ANALYSIS PLAN

MorphoSys AG  
MOR202C103

- Time to First Immunological Response (in months) prior to start of prohibited treatment (see definition in section 7.13.6) or progression, defined as  
[Date of first documented response of IPR, ICR or sICR (whichever is earlier) – Start date of study drug + 1 day]/30.4375
- Best overall immunological response (BIR) is defined when a subject is classified as having a IPR, ICR, or sIRC at any time during the trial but prior to start of prohibited treatment or progression. Responses for BIR are ordered as IPR < ICR < sICR. If a subject meets the criteria for more than one response category, the subject will be classified in the highest category.
- Time to BIR (in months), defined as  
[Date of BIR – Start date of study drug + 1 day]/30.4375
- Duration of Immunological response (in months), defined as  
[Date of death, PD or start of prohibited treatment (whichever is earlier) – Date of first documented response of IPR, ICR or sICR (whichever is earlier) + 1 day]/30.4375. Subjects with a response but no date of death, PD or start of prohibited treatment at the time of analysis cut-off will be censored at the date of last response assessment. Subjects without a response of IPR, ICR or sICR are assigned a duration time of zero.

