#### **8.8.5. Withdrawal due to Use of Prohibited Therapy [Immunosuppressive Therapy]**

Subjects starting on prohibited IST other than MOR202 will be withdrawn from the clinical trial. If withdrawn in the treatment phase, these subjects will immediately be scheduled for their EOT visit (at least 28 days after the last MOR202 dose) and will not enter the follow-up phase.

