### Proteinuria Response

Proteinuria responses are reflected by the reduction of proteinuria as measured by UPCR. Based on the proteinuria responses, the following response categories are defined by this clinical trial:

- Proteinuria Complete Response (Prot-CR): Reduction of proteinuria to less than 0.5 g/g, serum albumin within the reference range (3.5 – 5.2 g/dL) and stable eGFR (at least 80% of baseline)
- Proteinuria Partial Response (Prot-PR): Reduction by at least 50% of UPCR at a given visit compared to baseline, proteinuria below 3.0 g/g and stable eGFR (at least 80% of baseline), but not meeting Prot-CR

The following variables related to proteinuria responses are defined as follows.

Overall Proteinuria Response (OPR), defined as subjects achieving either Prot-CR or Prot-PR as a response (irrespective of start of prohibited medication or progressive disease prior to the proteinuria response).

Time to First Proteinuria Response (in months) prior to start of prohibited treatment or progression, defined as

[Date of first documented response of Prot-CR or Prot-PR (whichever is earlier) – Start of study drug + 1 day]/30.4375

Best Proteinuria Response (BPR) for a subject is defined when a subject is classified as having a Prot-CR or Prot-PR at any time during the trial but prior to start of prohibited treatment or progression. Responses for BPR are ordered as Prot-PR < Prot-CR. If a subject meets the criteria for more than one response category, the subject will be classified in the highest category.

Time to BPR (in months), defined as

[Date of BPR – Start date of study drug + 1 day]/30.4375

Duration of Proteinuria Response, defined as

[Date of death, PD or start of prohibited treatment (whichever is earlier) – Date of first documented response of Prot-CR or Prot-PR (whichever is earlier) + 1 day]/30.4375. Subjects with a response but no date of death, PD or start of prohibited treatment at the time of analysis

cut-off will be censored at the date of last response assessment. Subjects without a response of Prot-CR or Prot-PR are assigned a duration time of zero.

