#### 7.13.4. Disease progression

##### Progressive Disease

Progressive Disease (PD) is defined as a decrease of eGFR by more than 30% of baseline eGFR, or increase in UPCR by more than 50% from baseline value and less than 10% decline of anti-PLA2R antibody titres compared to baseline.

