#### Main Analysis

The main analysis will be conducted on FAS. The following information will be presented by cohort and overall:

- Number (%) of subjects achieving a BIR of IPR at any time during the trial
- Number (%) of subjects achieving a BIR of ICR at any time during the trial
- Number (%) of subjects achieving a BIR of sICR at any time during the trial
- BIRR along with the 95% confidence interval (CI, using the Clopper-Pearson exact method)
- Number (%) of subjects with a BIR of PD at any time during the trial
- Number (%) of subjects classified as Non-responder

For each visit available, the number and percentages of subjects in each of the response categories will be tabulated, including missing response evaluations and subjects with a progressive disease. Subjects, who are not classified in either response category or progressive disease will be tabulated as “*Non-Responders*”. Subjects with no post-baseline assessment of response will be included as “*Non-Responders*”.

If a subject achieves several responses, the subject will be tabulated in the highest achieved response category.

No formal hypothesis testing will be conducted.

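### Duration of response has no end event for losing the response, so a responder who relapses without PD, prohibited treatment or death is censored as if still responding

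*SAP*

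**What the plan says.** SAP 7.13.3 starts duration of immunological response at the first documented IPR, ICR or sICR and ends it at "Date of death, PD or start of prohibited treatment (whichever is earlier"). Responders with none of these "at the time of analysis cut-off will be censored at the date of last response assessment". Duration of proteinuria response follows the same rule from the first Prot-PR or Prot-CR. Non-responders are given a duration of zero.

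The states involved are defined as follows:

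- **IPR:** "Reduction of anti-PLA2R antibody titres by at least 50% compared to baseline". ICR needs a titre below 14.0 RU/mL; sICR adds a negative immunofluorescence test.
- **Prot-PR:** UPCR at least halved from baseline, with "proteinuria below 3.0 g/g and stable eGFR (at least 80% of baseline), but not meeting Prot-CR".
- **PD (SAP 7.13.4):** there are two routes. The renal route is a "decrease of eGFR by more than 30% of baseline eGFR". The alternative route combines proteinuria with titre and requires an "increase in UPCR by more than 50% from baseline value and less than 10% decline of anti-PLA2R antibody titres compared to baseline".

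For the by-visit tables, SAP 10.1 says: "Subjects, who are not classified in either response category or progressive disease will be tabulated as" Non-Responders. Protocol 8.8.5 adds that "Subjects starting on prohibited IST other than MOR202 will be withdrawn from the clinical trial".

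**The concern.** A duration of response should stop when the response stops. Here it stops only at PD, prohibited treatment or death. Response and PD are both measured against baseline, and the region between them is wide. A subject can leave every response category, sit in that region to the end of the trial, and be censored as though still in response.

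This matters because the protocol treats the event as important. Protocol 6.1.1 describes sustained or re-emerging antibody positivity as a negative predictor of outcome, and Protocol 8.8.3 foresees subjects in confirmed sICR turning positive again. According to the SAP document history (version 3.0), duration of response was added to give more information on efficacy. As defined, it misses re-emergence unless a listed event also occurs. It also conflicts with SAP 10.1, under which the same subject is a Non-Responder at the same visit.

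**Working it through.** The documents give no figure for duration of response, so there is none to reproduce. The check has three parts.

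**1. Does PD cover loss of response?** Assume a baseline titre of 200 RU/mL, UPCR 6.0 g/g and eGFR 90. IPR then needs a titre of 100 or less. Prot-PR needs UPCR at least halved and below 3.0, with eGFR at least 72. PD needs eGFR below 63, or UPCR above 9.0 together with a titre above 180.

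| Titre / UPCR / eGFR | IPR | Prot-PR | PD |
|---|---|---|---|
| 200 / 6.0 / 90 | no | no | no |
| 120 / 6.0 / 90 | no | no | no |
| 60 / 2.5 / 67.5 | yes | no | no |
| 181 / 9.1 / 90 | no | no | yes |
| 60 / 2.5 / 62 | yes | no | yes |

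The first row is a complete return to baseline and is not PD. A rise in titre alone is never PD, whether the rule is read as eGFR or (UPCR and titre), or as (eGFR or UPCR) and titre. The third row loses Prot-PR because eGFR is at 75% of baseline, which lies between the 80% and 70% limits.

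**2. Effect on one subject.** The SAP formula is (end day − first response day + 1)/30.4375. Days come from the protocol's Schedule of Assessments. Assume first IPR on Day 29, last assessment on Day 366 and no listed event. The SAP records (366 − 29 + 1)/30.4375 = 338/30.4375 = 11.10 months, censored, in every row.

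| Loss first seen | Time to loss (months) | Excess = (366 − loss day)/30.4375 |
|---|---|---|
| Day 85 | 57/30.4375 = 1.87 | 9.23 |
| Day 113 | 85/30.4375 = 2.79 | 8.31 |
| Day 141 | 113/30.4375 = 3.71 | 7.39 |
| Day 169 (EOT) | 141/30.4375 = 4.63 | 6.47 |
| Day 267 (FUV) | 239/30.4375 = 7.85 | 3.25 |
| Day 366 (EOS) | 338/30.4375 = 11.10 | 0 (status changes only) |

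For first Prot-PR on Day 85 the SAP records 282/30.4375 = 9.26 months. Loss at Day 169 is 85/30.4375 = 2.79 (excess 6.47), and loss at Day 267 is 183/30.4375 = 6.01 (excess 3.25).

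**3. Effect on a summary (illustration).** Assume 12 responders, of whom L lose response before Day 366 and c of those L also have a listed event before then. The share shown in response just before Day 366 is (12 − c)/12 under the SAP and (12 − L)/12 if loss counts.

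| L | SAP, c = 0 | SAP, c = L/2 | Loss counted |
|---|---|---|---|
| 2 | 100% | 92% | 83% |
| 4 | 100% | 83% | 67% |
| 6 | 100% | 75% | 50% |

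With c = L the shares agree. Now take all 12 responding first on Day 29, with L = 4 lost at Day 169 and c = 0. Counting loss, the Kaplan-Meier curve falls to 8/12 = 0.667 at 4.63 months, so Q1 is 4.63 months. Under the SAP there are no events and Q1 is not reached. Summarized as a plain duration, the mean is (8 × 11.105 + 4 × 4.632)/12 = 8.95 months against 11.10.

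**The case against.** **Limited weight.** Duration of response is not a primary, key secondary or secondary endpoint, nothing is tested, and the best immunological response rate is unaffected. The formula is stated openly, so it can be called a time-to-failure variable with an imprecise name. All of this stands and keeps the point from being more serious. It does not make the name accurate.

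**Loss is visible elsewhere.** SAP 10.1 gives by-visit tables and listings. SAP 10.2 gives individual UPCR plots with reference lines at ±50%, and the document history mentions similar plots for titres. With about 30 subjects, rebounds will be seen. These outputs do not correct the duration result, which may be quoted alone. Starting prohibited therapy also captures some relapses, but not loss of response by itself.

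**Redaction.** SAP 10.6, where the document history places the duration analysis, is blacked out, so the type of summary is unknown. That limits what can be said about reported results. The definitions in 7.13.3 are nevertheless complete, with start, end events and censoring, and do not refer to 10.6 for a further end event.

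**Another reading of the censoring date.** If the last response assessment means the last visit still in response, the excess months disappear: loss seen at Day 85 would be censored at Day 57, (57 − 29 + 1)/30.4375 = 0.95 months. The loss would still be censored rather than counted, so Kaplan-Meier would still show no event. The similar wording in the 7.13.5 censoring table favours the reading used above.

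**An unconfirmed loss rule could err the other way.** One titre at 51% of baseline, or one eGFR at 79% with UPCR still halved, would end the response. This is fair, and the new definition has to address it.

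**Conclusion.** The concern holds and should be fixed. The variable is the time from first response to PD, prohibited treatment or death, and it overstates durability whenever response is lost before one of those events. For a first response on Day 29 the overstatement runs from 0 months (loss seen at EOS) to 9.23 months (loss seen at Day 85), with the loss censored instead of counted. These figures assume visits on the scheduled days, a last assessment on Day 366 and no listed event. The gap in the definition is certain from the text. Its effect on the reported result is not, because the number of responders who lose response without a listed event is not in the documents and the summary in SAP 10.6 cannot be seen.

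**What to change.** - Add a duration of response in responders only, running from first response to the earliest of: the first assessment meeting no response category (none of IPR, ICR, sICR; or neither Prot-PR nor Prot-CR), PD, prohibited treatment, or death. Otherwise censor at the last response assessment, whatever the status there.
- State whether loss must be confirmed. If it must, say how a loss first seen at EOS is handled, since no scheduled visit follows. Also state whether a fall in eGFR alone ends a proteinuria response, and how missing components are treated.
- Keep the present variable beside it, relabelled as time from first response to PD, prohibited treatment or death.
- If the zero durations enter any summary, show responders separately.

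Two smaller items can be handled in the same edit. The text of SAP 7.13.5 censors drop-outs without an event at trial discontinuation, while its table uses the last response assessment; these should be aligned. A cumulative incidence estimate of time to response, with PD, prohibited treatment and death as competing events, could optionally sit beside Kaplan-Meier.

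The cost is SAP wording, one derived variable per response type and a relabel. The data already exist: titres at every visit, and 24-hour UPCR at Day 85, EOT, FUV and EOS after baseline. The trial is open-label, and the version 6.0 entry in the SAP history (19.09.2022) suggests that EOT and EOS data were already in hand. The change should therefore be dated, identified as late and described in the study report, in line with SAP section 4. Durability will look less favourable, and with 14 weeks between follow-up visits the date of loss will be coarse, more so with a confirmation rule.
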